#### **9.4.10 Image Warehouse and Final Deliverables**

All imaging data will be maintained in a secure environment. The imaging core laboratory will maintain a centralized image archive that will contain every imaging examination received from the clinical investigators for the study. Measurements will also be stored so that these data may be audited if necessary. The resulting database will be transferred to Guerbet after database lock for archiving.

The CDs/DVDs produced to record the ROIs (for off-site read only) are to be used for SI measurements and will be given to Guerbet at the end of the study once the off-site readers would have completed all the images reads.

### **9.5 Other Centralized Study Procedures**

#### **9.5.1 Clinical laboratory parameters**

A central laboratory will be used for all scheduled laboratory tests in this study except for the pregnancy test which will be done locally and eGFR which will be assessed locally and centrally. The investigator will be provided with a list of normal ranges prior to the start of the study. The central laboratory will provide the necessary kits to collect the blood samples and will also provide appropriate information regarding shipping of the samples.

Care should be taken during blood sampling in order to avoid potential generation of false positive blood value (e.g., by inappropriate use of the tourniquet or forceful withdrawal of blood). Each original laboratory report will be filled with the subject's source document.

All laboratory reports must be promptly reviewed by the Investigator, and upon review, initialed and dated by the Investigator. Change(s) in post-dose test values considered clinically significant, which would require either additional control or therapy, must be documented in the subject's source document and, in case of disturbing or influencing factor(s) on values/samples, details of the appropriate value(s) and the source of disturbance or influence (e.g. quality of sample, co-treatment etc.) are to be recorded. All values considered clinically significant will be reported as AEs.

Laboratory samples obtained for this study will be used only for this study. Samples obtained in this study will not be retained or used for any other purposes.

#### **9.5.2 Centralized assessment of ECG**

The 12-lead ECGs will be sent to the ECG core laboratory continuously during the course of the study for evaluation by an independent cardiologist. The following parameters will be evaluated for individual subjects and time points:

- RR interval and heart rate
- Intervals: PR, QRS, QT [plus calculated QTc (Fridericia and Bazett methods)]
- ST segments, T-wave morphology, U-wave
- Global morphology

The QTc is the heart rate corrected QT interval (calculation according to Fridericia and Bazett method).

The ECG core laboratory will record whether the cardiologist is unable to evaluate the ECG. A comment field will be provided for the cardiologist to indicate factors that effected the interpretation; e.g. lead reversal.

All ECGs changes considered as abnormal and clinically significant will be reported as AEs.

For ECGs a notable QTc change is defined as a QTc (Fridericia's or Bazett's) interval of greater than 450 ms for males and females – all such ECGs will be flagged by the core laboratory's cardiologist and require assessment for clinical relevance by the Investigator.

 CONFIDENTIAL	Protocol No. GDX-44-004 Version No. 2.0 (Protocol including amendment n°1) Date: 11 July , 2016	 Page 52 / 84
---------------------------------------------------------------------------------------------------	----------------------------------------------------------------------------------------------------------	-----------------------------------------------------------------------------------------------------

## 10 SAFETY REPORTING

### 10.1 Adverse Event

#### 10.1.1 *Definition of Adverse Event*

An Adverse Event (AE) is any untoward medical occurrence in a patient or clinical investigation subject administered a pharmaceutical product and which does not necessarily have to have a causal relationship with this treatment.

An adverse event (AE) can therefore be any unfavourable and unintended sign (including an abnormal laboratory finding, for example), symptom, or disease temporally associated with the use of a medicinal product, whether or not considered related to the medicinal product.

Any disease identified and diagnosed by study contrast-enhanced MRI will not be considered as AE.

#### 10.1.2 *Recording/Collection of Adverse Events*

The Investigator or his/her designee will invite the subject to report any experienced abnormality as part of the usual clinical follow-up.

All Adverse Events, whether considered as related or not to the Investigational Medicinal Product and/or the imaging procedure should be reported in the medical file and the eCRF and monitored from onset to resolution or stabilization of sequelae. If no follow-up is performed, the investigator must provide a justification in the medical file.

In order to ensure complete safety data collection, all Adverse Events occurring during the time of the subject's participation in the study, must be reported and monitored even if no IMP was administered. The investigator shall document all Adverse Events in the medical file and the appropriate section of the eCRF.

As a reminder the subject's participation is defined as the period from the screening visit (ICF signature) to the last study visit and defined in [Section 11](#) in case of premature discontinuation.

Safety information is to be collected by the investigator with the same procedure as Adverse Events: treatment errors and uses outside what is foreseen in the protocol, including misuse and abuse of the product, suspicion of transmission of an infectious agent via an IMP, overdose (symptomatic or not), all reports of pregnant or breastfeeding women exposure even if uneventful, all reports of suspected drug-drug interaction with another product (symptomatic or not).

As an exception, as the study aims to assess the effective dose of P03277, doses with lesser efficacy are expected and will be considered while analyzing the primary endpoint.

In this protocol, the overdose is defined as more than 0.3 mmol/kg for P03277 and more than 0.2 mmol/kg for MultiHance®. Any overdose, with or without adverse event, will be reported as AE and, in addition, on SAE form if the associated event is serious.

#### 10.1.3 *Description of Adverse Events*

The following guidelines and definitions should be used by the investigator for the description of an AE when reporting information:

- **Nature of AE:** preferably an overall diagnosis or syndrome, rather than individual symptoms or signs. The investigator must report AE using standard medical terminology. The same terms should be used in the source documentation and in the eCRF.

- **Date and time of onset:** date and clock time of the AE start.
- **Intensity:**
  - Mild: the subject is aware of the sign or symptom, but it does not interfere with her/his usual daily activities and/or it is of no clinical consequence.
  - Moderate: the AE interferes with the usual daily activities of the subject or it is of some clinical consequence.
  - Severe: the subject is unable to work normally or to carry out his/her usual daily activities, and/or AE is of definite clinical consequence.
- **Date of the event end (or consolidation):** The real date of event end will be entered if the event has come to its end on the date of end of subject's follow-up. If the AE is still ongoing by the time of end of study follow-up for the subject (i.e. last study visit), the subject should be followed-up until AE resolution or a justification should be provided by the Investigator (i.e. chronic disease) in the medical file.
- **Causal relationship to the Investigational Medicinal Product:**
  - Related: the definition of adverse reaction implies a reasonable possibility of a causal relationship between the event and the IMP. This means that there are facts (evidence) or arguments to suggest a causal relationship.
  - Not related: Applicable when no IMP has been administered (pre-administration period) or when no causal relationship exists between the study drug and the event, but an obvious alternative cause exists (e.g. the subject's underlying medical condition or concomitant therapy).
- **Causal relationship to a study procedure – apart from imaging procedure:**
  - Related.
  - Not related.
- **Outcome:**
  - Recovered/Resolved: the AE is no longer present at any intensity.
  - Recovered/Resolved with sequelae: the AE is resolved but residual effects are still present.
  - Not Recovered/Not Resolved: the AE is still present at the last contact with the subject.
  - Fatal: this AE caused or directly contributed to subject's death.
- **Action taken with regard to administration of the IMP:**
  - No action: for AE occurring during the pre-treatment/procedure or post-treatment/procedure period, or if the Investigational Medicinal Product dosing/administration remained the same in spite of AE being present.
  - Action taken :
    - Study treatment unblinding
    - IMP definitively stopped: IMP was permanently discontinued.
- **Other action taken:**
  - AE-targeted treatment: the subject took a treatment (either prescription or non-prescription) specifically for this AE. The drug(s) should be reported in the appropriate section of the eCRF ("concomitant drug" section)
  - Other AE-targeted action: subject used other therapeutic measures (e.g. ice, heating pad, brace, cast...) or subject underwent a procedure (physiotherapy,

Guerbet    CONFIDENTIAL	Protocol No. GDX-44-004 Version No. 2.0 (Protocol including amendment n°1) Date: 11 July , 2016	 Page 54 / 84
---------------------------------------------------------------------------------------------------------------------------	----------------------------------------------------------------------------------------------------------	-----------------------------------------------------------------------------------------------------

additional laboratory test...) for this AE. The therapeutic measure(s) should be reported in the appropriate section of the eCRF.

- **Assessment of the seriousness of the AE:** see [Section 10.2](#) for SAE definition.

## 10.2 Serious Adverse Event

### 10.2.1 Definition of Serious Adverse Event

A Serious Adverse Event (SAE) is any untoward medical occurrence that at any dose:

- Results in death
- Is life-threatening
- Requires hospitalization or prolongation of hospitalization
- Results in persistent or significant disability or incapacity
- Is a congenital anomaly or birth defect
- Is medically important: adverse events that are not immediately life-threatening or do not result in death or hospitalization but may jeopardize the subject or may require intervention to prevent one of the other outcomes listed in the definition above, should also be considered serious.

Life-threatening in the definition of a serious adverse event refers to an event in which the subject was at risk of death at the time of event; it does not refer to an event which hypothetically might have caused death if it were more severe.

Medical judgment should be exercised in deciding whether an adverse event/reaction is serious in other situations. In case of a SAE, the investigator is responsible for the measures to be taken to ensure the safety of the study participants.

The following safety issues qualify for immediate reporting to Guerbet since they may alter the current benefit-risk assessment of an investigational medicinal product, or would be sufficient to consider changes in the study drug administration or in the overall conduct of the study:

- Any post-study related adverse event that occurs after the subject has completed the study and that is considered as related to the Investigational Medicinal Product by the investigator (causality not excluded).
- Any new event likely to affect the safety of the subjects and that may be related to the conduct of the study or the development of the study drug such as:
  - A SAE which could be associated with the study procedures and which could modify the conduct of the study
  - A significant hazard such as an unusual failure in efficacy.
  - A new finding from a newly completed animal study.

 CONFIDENTIAL	Protocol No. GDX-44-004 Version No. 2.0 (Protocol including amendment n°1) Date: 11 July , 2016	 Page 55 / 84
---------------------------------------------------------------------------------------------------	----------------------------------------------------------------------------------------------------------	-----------------------------------------------------------------------------------------------------

**Severe / Serious:** the term “severe” is often used to describe the intensity (severity) of a specific event (within the scale mild, moderate, severe). The event itself, however, may be of relatively minor medical significance. This is not the same as “serious”, which is based on subject/event outcome or action criteria.

In this protocol, the following situations will not be considered as SAE, providing that they are clearly documented as such in the subject's source data:

- Any hospitalization that had been planned before the study and that will take place during the study, provided there is no aggravation of the disease to which it is related.
- Hospitalizations, which are not associated to an adverse event (such as hospitalization for checkup).

#### ***10.2.2 Procedure for Reporting Serious Adverse Events***

SAEs occurring from ICF signature until completion of the study for each subject are to be reported to Guerbet Pharmacovigilance department.

The investigator **must immediately and within 24 hours** forward to Guerbet Pharmacovigilance department a duly completed SAE report form provided by Guerbet with study documents, even if it is obvious that more data will be needed in order to draw any conclusion:

- **By Fax #:** [name]
- or
- **by e-mail to:** [[contact]](mailto:[contact])

In case of emergency, Guerbet Pharmacovigilance department may be contacted at:

**[name].**

Additional information (e.g., autopsy, lab reports...) may be required by Guerbet in a timely fashion to ensure accurate follow-up and assessment of each case and should be forwarded, anonymized, with a new form specifying basic information (follow-up number, subject details and number, adverse event, study product, causal relationship) and the new information.

The initial and follow-up reports shall identify the study subject by his/her identification (subject ID) number assigned for the purpose of the study.

In order to allow the assessment and eventual subsequent regulatory reporting of the case, the following minimum information should be filled in:

- Subject's details including age, sex and subject's study enrolment number
- Subject's medical history relevant to the assessment of the event
- Type of event by reporting a diagnosis, or if not available, symptoms
- Date and time to onset of the event
- End date of the event (will be reported in a follow-up report if the event is still ongoing at the time of first notification)
- Name of the investigational drug or procedure, date and time of administration, dose and volume administered
- Causal relationship to the investigational drug or procedure (mandatory)
- Outcome at the time of reporting

Any event leading to a SAE report should be reported in the medical file and in the adverse event section of the eCRF as requested in [Section 10.1.2](#)

 CONFIDENTIAL	Protocol No. GDX-44-004 Version No. 2.0 (Protocol including amendment n°1) Date: 11 July , 2016	 Page 56 / 84
---------------------------------------------------------------------------------------------------	----------------------------------------------------------------------------------------------------------	-----------------------------------------------------------------------------------------------------

SAEs should be followed up by the investigators until complete recovery of the subject or, if not possible, until stabilization of sequelae. The investigator may be requested by Guerbet to provide follow-up information in order to comply with current regulations as well as for comprehensive assessment purposes.

SAEs associated with study procedures are to be notified using the same reporting procedure as described above.

In addition, if occurring after the end of the subject's follow-up period defined for this study (i.e. within 1 day post second IMP administration), serious adverse and/or unexpected events that the Investigator thinks may be associated with the study treatment/procedure must be reported to Guerbet regardless of the time between the event and the end of the study.

According to local requirements, Guerbet or its representatives will communicate relevant safety information to the appropriate agency(ies), IEC and/or all active investigators, as it becomes available.

The transmission of the information to Guerbet does not release the investigator from his responsibility to inform the regulatory authorities, if applicable.

### **10.3 Pregnancy and Adverse Events of Special Interest**

In addition to the above AEs, the special situations described below should be handled with the same procedure as the SAE reporting procedure.

#### ***10.3.1 Pregnancy***

Any pregnancy (with or without an AE of women participating in the study and partners of men participating in the study) that occurs during the study and up to 7 days post visit 4 must be reported to Guerbet via the SAE report form.

Any participating subject who becomes aware of a pregnancy (subject's or subject's partner) during study participation should inform immediately the investigational site. The female subject should be immediately withdrawn from IMP administration.

Pregnancy will be monitored until completion or termination. If the pregnancy continues to term, the outcome (health of infant up to 8 weeks of age) will be reported to Guerbet using specific forms "history and start of pregnancy" and "course and outcome of pregnancy" that will be provided to the investigational sites. Any complication of pregnancy will be reported as an AE or SAE, as appropriate.

#### ***10.3.2 Adverse Events of Special Interest***

An Adverse Event of Special Interest (AESI) is an AE designated by Guerbet for transmission to Pharmacovigilance in the same time frame as an SAE.

The AESI for this protocol is the following: Nephrogenic Systemic Fibrosis (NSF).

Also, any suspicion of transmission of an infectious agent via an IMP should be considered as a serious and processed as an SAE.

In addition, any adverse reaction resulting from an occupational exposure (i.e. exposition to IMP of an investigating site staff member) may be directly reported to Guerbet.

Guerbet   	Protocol No. GDX-44-004 Version No. 2.0 (Protocol including amendment n°1) Date: 11 July , 2016	████████████████████ Page 57 / 84
CONFIDENTIAL		

#### **10.4 Unblinding Procedures**

The investigator may, under exceptional circumstances unblind the individual study treatment group if he/she considers that this procedure is relevant to the safety of the study subject. Individual study treatment unblinding is described in [Section 5.3.3](#). Unblinding must be documented in the subject medical file, completed in the SAE form sent to Guerbet Pharmacovigilance department, if applicable.

Suspected Unexpected Serious Adverse Reaction (SUSARs) will be unblinded by Guerbet Pharmacovigilance Department for regulatory reporting purposes; however, these SUSARs will remain blinded to the investigator and to Guerbet personnel responsible for study management, data analysis, and interpretation of results at the study's conclusion.

 CONFIDENTIAL	Protocol No. GDX-44-004 Version No. 2.0 (Protocol including amendment n°1) Date: 11 July , 2016	 Page 58 / 84
---------------------------------------------------------------------------------------------------	----------------------------------------------------------------------------------------------------------	-----------------------------------------------------------------------------------------------------

## 11 PREMATURE DISCONTINUATION OF THE STUDY

### 11.1 Premature Discontinuation of the Study per Guerbet Decision

Guerbet reserves the right to discontinue the study at any time for medical, administrative or other reasons.

Guerbet will inform the relevant authorities in each country, the ethics committees, the study site investigators, pharmacists, if applicable and hospital authorities according to the regulatory texts in force.

### 11.2 End of Study Participation for a Subject

Screening failures: Subjects who signed the informed consent form and discontinue before Visit 2 (first contrast agent injection and MRI procedures) will be considered screening failures.

If a subject discontinues before Visit 2, the IWRS must be notified and only the reason for being screening failure will be documented on the source document and in the eCRF (see [section 15.3.2](#))

Criteria for premature discontinuation of subjects:

- Adverse Event (according to the investigator's judgment);
- Withdrawal of subject's consent;
- Subject lost to follow-up (date of last contact will be documented in the medical file and the eCRF). Any effort will be undertaken to know the reason for this loss to follow-up and/or to exclude any adverse reaction as this reason. This will be documented in the medical file;
- Any treatment or medical procedure (e.g. chemotherapy, radiotherapy, biopsy or surgery etc...) between the two MRIs;
- At the discretion of the investigator if, for example, the subject safety or well-being is not compatible with study continuation;

Specific subjects study stopping rules:

If any of the events described below occur, injection of IMPs should not be done and the subject should be discontinued from the study:

- Renal toxicity characterized by an increase in serum creatinine by more than 25% or 0.5 mg/dl (44 µmol/l) and/or an increase in serum cystatin C by more than 25% compared to the baseline value
- QTc Bazett or QTc Fridericia >500 ms or an increase of > 60 ms over baseline
- Any events which investigator or Guerbet considers raising a significant concern

The data to be reported in the eCRF for subjects subsequently discontinuing from the study are detailed in the protocol [section 15.3.2](#).

For subjects withdrawn from the study, all data available at the time of withdrawal will be reported in the medical file and the eCRF (e.g.: inclusion data, safety data, administration data, imaging data, reason for withdrawal...). The investigator must make every effort to collect and record all follow-up safety information (i.e., AEs and injection-site tolerance, as appropriate), unless the subject withdraws consent for further data collection/participation for/in the study.

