## Statistical methods

Student t-test using Holm's step-down method in a Multiple Comparisons Design with 0.025 type-one error will be used to evaluate the dose-response of P03277 for each Independent Blinded Reader (IBR) with regards to the CNR value as the primary endpoint. The post-CNR value will be normalized by the pre-CNR value calculated on the same basis.

Descriptive statistics will summarize demographics, efficacy and safety data. Dose/response relationship of P03277 will be investigated for each IBR.

[figure not shown]
Table 1: Study Flow Chart

Evaluation/ procedure	Screening (V1)	Inclusion V2  (Baseline  ) Contrast injection P03277 or MultiHance ®				Safety follow up (V3) Post injection P03277 or MultiHance ®	V4  Contrast injection P03277 or MultiHance ®				Safety follow up (V5) Post injection P03277 or MultiHance ®
		≤7 days	Prior to MRI	MRI	45± 15min	2-4 hrs	1 day after V2	Prior to MRI	MRI	45± 15min	2-4 hrs
Time Point											
Informed consent signature	X										
Eligibility criteria	X	X									
Demographic data	X										
Medical history	X										
Physical examination 	X										
Body weight		X						X			
Concomitant treatments	X		X				X		X		X
Pregnancy test 	X	X						X			
Local e-GFR evaluation 		X						X			
Clinical laboratory parameters 		X					X	X			X
Urinalysis (Dipstick)		X					X	X			X
Vital signs (BP, PR) 	X		X	X	X		X		X	X	X
12-lead ECG 		X		X	X		X	X		X	X
IMP injection			X						X		
Images acquisition			X						X		
IWRS 	X	X					X	X			X
Injection-site tolerance 			X	X	X		X		X	X	X
Subject treatment plan evaluation				X					X		
Adverse events (AEs) 							X				

[figure not shown]
- (1) MRI procedures, at V2 and V4, should be performed on the same day of IWRS connection and contrast agent injection.
- (2) Urine or serum pregnancy test (if applicable) is to be done on site, and results must be available prior to IWRS connection and administration of P03277 and MultiHance®
- (3) eGFR is to be done locally, and results must be available prior to IWRS connection and administration of P03277 and MultiHance®
- (4) Clinical laboratory parameters will be analysed by the central laboratory: haematology and biochemistry, Cystatin C, see [Section 9.5.1](#) for details

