During the course of the study, the two teams should not exchange any information regarding the subjects enrolled and the IMPs (nature, order of administration, dose). The subjects' files with unblinded data should not be filled with the subjects medical and study files in order to not break the blind. The unblinded documentation should be stored shielded from the view of the blinded staff. An initial shipment of IMPs will be sent to the investigational sites after having received regulatory authorization(s)/ethical approval(s) as per local requirements. Additional shipments will be sent according to subject recruitment progress of a given investigational site. The site should ensure to have enough IMPs before including a new subject. The site can log onto IWRS to know the IMPs stock status.

IMP receipt will be acknowledged by the investigator (or any designated person in his/her team) via IWRS.

Subject numbers will be sequential within each center.

At visit 2 and visit 4, once the eGFR and pregnancy test have been checked, the site should log onto the IWRS which will allocate IMP(s) number available at the site. This/these IMP(s) will correspond to the allocated treatment arm and to the contrast medium allocated for the enhanced MRI procedure.

In case one IMP breaks or becomes non-sterile or is not available, or any problem of IMP allocation (e.g. wrong IMP administered to the subject), the site must immediately report the incident into IWRS and to Guerbet's representative in order to ensure that all corrective actions are taken. Corrective actions may include transferring the IMP to quarantine to prevent further IMP allocation by the site until the

 CONFIDENTIAL	Protocol No. GDX-44-004 Version No. 2.0 (Protocol including amendment n°1) Date: 11 July , 2016	 Page 30 / 84
----------------------------------------------------------------------------------------------------------	----------------------------------------------------------------------------------------------------------	-----------------------------------------------------------------------------------------------------

situation is under control again. Detailed instructions can be found in the IWRS manual provided to the sites.

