**Procedures to be followed after MRI examination:**

The subject will stay at the study site for at least 2-4 hours after the MRI examination is completed and the following procedures will be performed:

- Use/change of concomitant treatments during the visit;
- Vital signs (systolic and diastolic Blood Pressure and PR) and 12-lead ECG (triplicate ECGs, 3 measurements taken at approximately 1 min intervals) will be obtained 45 minutes  $\pm$  15 minutes and between 2-4 hours after the injection of contrast agent. If significant changes in vital signs occur, vital signs should be recorded more frequently and for as long as necessary, to ensure that the changes are resolved, and/or that the subject is stable;
- Injection-site tolerance (burning, pain, eruption, extravasation, inflammation, or other) is to be assessed during the injection , 45 minutes  $\pm$  15 minutes and between 2-4 hours after the injection of contrast agent;
- Assessment of AEs will be documented;
- Evaluation of the potential impact of IMP-enhanced MRI on subject treatment plan;

 CONFIDENTIAL	Protocol No. GDX-44-004 Version No. 2.0 (Protocol including amendment n°1) Date: 11 July , 2016	 Page 44 / 84
----------------------------------------------------------------------------------------------------------	----------------------------------------------------------------------------------------------------------	-----------------------------------------------------------------------------------------------------

- Safety follow-up visit (Visit 3) needs to be scheduled 1 day post contrast agent injection;
- Scheduling of the second MRI examination (visit 4) between 2 days and 14 days post visit 2.

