#### ***9.1.3 Safety Visit – Visit 3 (1 day post visit 2)***

During this visit, the following assessments or tasks will be performed:

- Use/change of concomitant treatments will be documented;
- Blood samples will be collected according to central laboratory manual;
- A urine dipstick will be done and the results will be documented on the source documentation;
- Vital Signs (systolic and diastolic Blood Pressure in supine position, PR) and 12-lead ECG (triplicate ECGs, 3 measurements taken at approximately 1 min intervals) should be recorded;
- Injection-site tolerance is to be evaluated;
- Assessment of AEs will be documented;
- IWRS connection to record the study visit;
- Remind the date of visit 4 to the subject.

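### No listed visit 4 step makes sure the central cystatin C result is known before the second injection that Protocol 11.2 would forbid

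*Protocol*

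**What the plan says.** Protocol 11.2 lists events after which no injection should be given and the subject leaves the study. The renal item is a creatinine rise of more than 25% or 0.5 mg/dL and/or "an increase in serum cystatin C by more than 25% compared to the baseline value". Cystatin C can therefore trigger the stop on its own. Footnote 10 of the flow chart (Protocol Table 1) defines baseline as the assessments before the first MRI at visit 2.

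**Where it is measured.** Protocol 9.5.1: "A central laboratory will be used for all scheduled laboratory tests in this study except for the pregnancy test which will be done locally". The same sentence makes eGFR the only test done both locally and centrally. Flow-chart footnote 4 agrees: "Clinical laboratory parameters will be analysed by the central laboratory: haematology and biochemistry, Cystatin C".

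**What must be known before injection.** Footnote 3: "eGFR is to be done locally, and results must be available prior to IWRS connection and administration of P03277" (and of MultiHance). Footnote 2 sets the same condition for the pregnancy test. Protocol 5.3.1: "At visit 2 and visit 4, once the eGFR and pregnancy test have been checked, the site should log onto the IWRS". Footnote 4 has no such condition. Section 9.1.4 asks for local creatinine and eGFR verification at visit 4, but for central blood only that it be collected.

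**Timing.** Visit 3 is one day after visit 2, and there "Blood samples will be collected according to central laboratory manual". Section 9.1.2 provides for "Scheduling of the second MRI examination (visit 4) between 2 days and 14 days post visit 2". Footnote 1 adds: "MRI procedures, at V2 and V4, should be performed on the same day of IWRS connection and contrast agent injection".

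**The concern.** A rule that forbids an injection works only if its trigger can be read before the injection. For the pregnancy test and local eGFR, the protocol says so explicitly. For cystatin C it sets the trigger and schedules the sample, but no supplied text makes visit 4 wait for the result.

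At stake is a second gadolinium injection given to someone who already meets a renal stopping criterion that the sponsor chose to set separately from creatinine. Section 13 also cites the stopping rules and the check points before the second MRI among several reasons for not setting up an independent monitoring committee, so those check points should work as described. The point concerns subject safety. It does not bear on the validity of the primary CNR comparison.

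**Working it through.** **Inputs**
- Visit 2 is day 0 and visit 3 is day 1 (Protocol 9.1.2, 9.1.3).
- Visit 4 is any of days 2 to 14, which is 13 permitted days (9.1.4). Visit 5 is one day after visit 4 (9.1.5).
- Central turnaround T, in whole days from the visit 3 draw, is not in the documents. It is assumed here to be 1 to 7.

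**The plan's own durations.** Shortest path: screening and visit 2 on day 0, visit 3 on day 1, visit 4 on day 2, visit 5 on day 3. Days 0 to 3 counted inclusively are 4 days, the stated minimum. Longest path: 7 + 14 + 1 = 22 elapsed days, the stated maximum. The 4-day minimum confirms that visit 4 on day 2 is a schedule the protocol allows.

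**Which sample can inform the rule.** The visit 2 sample is the baseline. The visit 4 central sample is drawn on the day of allocation and injection, so it would need a same-day central result. That leaves the visit 3 sample. The interval from its draw to visit 4 is 2 − 1 = 1 day at the shortest and 14 − 1 = 13 days at the longest.

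**How much of the window precedes the result.**
- Result day = 1 + T, counted as in hand if it arrives before allocation that day.
- Permitted visit 4 days before the result = (1 + T) − 2 = T − 1.
- Permitted days remaining if visit 4 waits = 14 − (1 + T) + 1 = 14 − T.

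| Assumed T (days) | Result day | Permitted days before result | Days left if visit 4 waits |
|---|---|---|---|
| 1 | 2 | 0 | 13 |
| 2 | 3 | 1 | 12 |
| 3 | 4 | 2 | 11 |
| 5 | 6 | 4 | 9 |
| 7 | 8 | 6 | 7 |

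These are counts of calendar days. They are not proportions of subjects, because the documents do not say how visit 4 dates will be spread over the window.

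**Whether a redraw fits.** If the first result is unusable and blood is redrawn on day 1 + T, the second result arrives on day 1 + 2T. The condition 1 + 2T ≤ 14 holds up to T = 6 (day 13) and fails at T = 7 (day 15).

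**Who is exposed.** Local creatinine is drawn at visit 4 before injection, and SAP 5.2.2 has a deviation line for a creatinine stop found on local measurements. Its cystatin C line refers to central measurements only. The gap therefore concerns subjects for whom all of these hold: cystatin C up by more than 25%, no qualifying local creatinine rise, local eGFR at least 60, and visit 4 before the central result.

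**The case against.** The strongest reply is that the protocol already forbids the injection. Section 11.2 bars it, section 3.4 makes investigators and sponsor responsible for applying the stopping rules, 9.5.1 requires prompt review of laboratory reports, and section 13 gives the DSMB a duty to see that the rules are applied. Sites also choose the visit 4 date within a 13-day range, so they can wait, and the visit 3 laboratory draw can reasonably be read as the intended check point. Local creatinine and eGFR cover most of the renal risk. Turnaround, sampling and allocation details may be in the central laboratory manual, the IWRS manual or the Data Safety Monitoring Plan.

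Much of this stands. A reader might infer that the protocol permits injection despite a known cystatin C rise, or that renal stops in general go unchecked. The documents support neither: a site that injected with such a result in hand would breach 11.2, and the creatinine limb can be read locally on the day. Nor can it be said that no hold exists anywhere, since those three documents were not supplied. The non-major status of a missed cystatin C stop in SAP 5.2.2 should not be read as a safety judgement either, because the SAP defines major by impact on the primary criteria.

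What does not stand is the idea that general duties close the gap. Nobody can apply a rule to a value not yet reported. Prompt review starts when the report arrives and sets no deadline relative to visit 4. The laboratory flags described in 7.2.8 mark values outside normal ranges, so a 25% rise within range need not be flagged. The SAP deviation line records a missed stop only afterwards.

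**Conclusion.** The concern holds in a limited form. On the supplied text, a site can complete every listed visit 4 step and inject before the cystatin C limb of 11.2 can be evaluated. This goes beyond missing operational detail, because a permitted visit 4 date can leave a stated safety rule inoperable.

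Its size depends on turnaround, which is assumed: none of the 13 permitted days precedes the result at T = 1, two do at T = 3 and six at T = 7. The number of subjects affected cannot be derived, and only an isolated cystatin C rise combined with an early visit 4 is exposed. The point should be addressed because the remedy uses a sample already being drawn. Confidence is medium, since a manual that was not supplied may already set the hold.

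**What to change.** In flow-chart footnote 4 and Protocol 5.3.1 and 9.1.4, require that the visit 3 central cystatin C and creatinine results be received and compared with the central visit 2 baseline before visit 4 IWRS connection, with visit 4 scheduled within days 2 to 14 accordingly. If a manual already sets this hold, cite it in those places instead.

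The sponsor should also state in advance what happens if the visit 2 baseline or the visit 3 result is unusable. For visit 3, the choice is between a redraw within the window and reliance on the local creatinine and eGFR check. A pre-injection baseline cannot be recovered after the first injection, so there the local check is the realistic option. An automatic ban on the second injection when no result is available is not needed; it would be a new discontinuation criterion.

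**Cost.** Protocol wording and one IWRS or checklist item. No routine extra sample is needed, although a redraw may mean an unscheduled attendance. Some visit 4 dates move later: at T = 3 the earliest becomes day 4, leaving 11 of 13 days. That gives slightly more time for lesion change or an intervening treatment, and possibly a few more non-evaluable subjects. The design carries 10 spare subjects per group of 60 (10/60 = 16.7%), shared with all other losses, and Protocol 8 and 11.2 allow a sample size increase if losses exceed expectation.
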